4.3. Definitions, Computations, and Conventions

4.3.1. Date of First Dose and Date of Last Dose of Study Drug

The date of the first dose of study drug is defined as the date a patient receives the first dose of study drug. The date of the last dose of study drug is defined as the date a patient receives the last dose of study drug.

4.3.2. Treatment Day

Treatment day will be calculated in reference to the date of the first dose of study drug. Treatment Day 1 corresponds to the date a patient receives the first dose of study drug. For assessments conducted on or after the date of the first dose of study drug, treatment day will be calculated as (assessment date – date of first dose of study drug + 1). There will be no Treatment Day 0. Efficacy and safety analyses will be based on treatment day, unless otherwise specified.

4.3.3. Treatment Period

The treatment period is defined as the period of time from the date of the first dose of study drug through the date of last dose. The treatment period per protocol is 48 weeks (Treatment Day 336). For patients in the leuprolide acetate treatment arm, treatment period ends 12 weeks after the last leuprolide acetate injection.

4.3.4. Treatment Duration

Treatment duration is defined as the duration of time from the date of the first dose of study drug to the date of the last dose of study drug, calculated as follows:

For relugolix treatment arm, treatment duration is:

$$(\text{Date of last dose of study drug} - \text{Date of first dose of study drug}) + 1.$$

For leuprolide acetate treatment arm, treatment duration is:

$$(\text{Date of last dose of study drug} - \text{Date of first dose of study drug}) + 84.$$

4.3.5. Baseline Value and Postbaseline Value

Both date and time of study drug administration and measurement will be considered when calculating baseline value. Unless otherwise specified, the baseline value is defined as the last measurement on or before the first administration date (if time is not available) of study drug. Or the baseline value is defined as the last measurement before the first administration date and time of study drug. Postbaseline value is defined as any measurement taken after the first administration of study drug. Change from baseline is defined as (postbaseline value – baseline value). If time is not available, then date only will be used.

4.3.6. Visit Windows

Visit windows will be used to associate assessments with a scheduled visit and will be used only for summarizing data by visit. Visit windows for each assessment are defined as shown in [Table 2](#). A separate set of visit windows for assessment of quality of life are defined in

Table 3. For both efficacy and safety assessments, the Treatment Day will be used to determine the associated visit window.

If more than one observation lies within the same visit window, the observation with the closest study day to the target study day will be used. If there are two observations equidistant to the scheduled target day, the earlier assessment will be used.

Table 2: Visit Windows

Visit	Start Day	Target Day	End Day
Week 1 Day 4 ^a	1	4	8
Week 3 Day 1	9	15	21
Week 5 Day 1	22	29	43
Week 9 Day 1	44	57	71
Week 13 Day 1	72	85	99
Week 17 Day 1	100	113	127
Week 21 Day 1	128	141	155
Week 25 Day 1	156	169	183
Week 29 Day 1	184	197	211
Week 33 Day 1	212	225	239
Week 37 Day 1	240	253	267
Week 41 Day 1	268	281	295
Week 45 Day 1	296	309	323
Week 49 Day 1	324	337	365
Safety Follow-up ^b	Date of last dose + 2 days in relugolix arm Date of last dose + 8 days in leuprolide arm	Date of last dose + 30 days	Date of last dose + 45 (59 ^d) days
60-Day Testosterone Recovery ^c	Date of last dose + 46 days	Date of last dose + 60 days	Date of last dose + 75 days
90-Day Testosterone Recovery ^c	Date of last dose + 76 days	Date of last dose + 90 days	Date of last dose + 119 days

Date of last dose in leuprolide acetate ends 12 weeks after the last leuprolide acetate injection.

^a Start day of Week 1 Day 4 only includes postbaseline assessments on or after the first dose.

^b The safety follow-up visit window will be restricted to assessments prior to the date of initiation of another investigational agent or hormonal therapy or surgical intervention, whichever occurs first.

^c Approximately 100 patients receiving relugolix and 50 patients receiving leuprolide acetate who complete the 48 weeks of study treatment and, in the opinion of the investigator, can remain off androgen deprivation therapy for 90 days will be included in the testosterone recovery 60- and 90-day follow-up visits.

^d For patients not enrolled in the testosterone recovery follow-up, the end day of safety follow-up visit can be extended to Day 59 after the date of last dose.

Table 3: Visit Windows for Assessments in Quality of Life

Visit	Start Day	Target Day	End Day
Week 5 Day 1	9	29	57
Week 13 Day 1	58	85	127
Week 25 Day 1	128	169	211
Week 37 Day 1	212	253	295
Week 49 Day 1	296	337	365
Safety Follow-up ^a	Date of last dose + 2 days in relugolix arm Date of last dose + 8 days in leuprolide arm	Date of last dose + 30 days	Date of last dose + 45 (59 ^c) days
60-Day Testosterone Recovery ^b	Date of last dose + 46 days	Date of last dose + 60 days	Date of last dose + 75 days
90-Day Testosterone Recovery ^b	Date of last dose + 76 days	Date of last dose + 90 days	Date of last dose + 119 days

Date of last dose in leuprolide acetate ends 12 weeks after the last leuprolide acetate injection.

^a The safety follow-up visit window will be restricted to assessments prior to the date of initiation of another investigational agent or hormonal therapy or surgical intervention, whichever occurs first.

^b Approximately 100 patients receiving relugolix and 50 patients receiving leuprolide acetate who complete the 48 weeks of study treatment and, in the opinion of the investigator, can remain off androgen deprivation therapy for 90 days will be included in the testosterone recovery 60- and 90-day follow-up visits.

^c For patients not enrolled in the testosterone recovery follow-up, the end day of safety follow-up visit can be extended to day 59 after the date of last dose.

4.4. General Rules for Missing Data

Handling of missing data for the efficacy endpoints is described in [Section 7](#).

4.4.1. By -Visit Endpoints

By-visit endpoints will be analyzed using observed data, unless otherwise specified. For observed data analyses, missing data will not be imputed and only the observed records will be included.

4.4.2. Adverse Events

The imputation rule for the safety analyses will be used to address the issues with partial dates. The imputed dates will be used to determine the treatment-emergent period. For adverse events with a partial date, available date parts (year, month, and day) of the partial date will be compared with the corresponding date components of the start date and end date of the treatment-emergent period to determine if the event is treatment emergent. When in doubt, the adverse event will be considered treatment emergent by default. The following rules will be applied to impute partial dates for adverse events:

If start date of an adverse event is partially missing, impute as follows:

- If both Month and Day are missing and Year = Year of treatment start date, then set to treatment start date, as long as adverse event end date is not prior to treatment start date;
- If both Month and Day are missing and Year \neq Year of treatment start date, then set to January 1;
- If Day is missing and Month and Year = Month and Year of treatment start date, then set to treatment start date, as long as adverse event end date is not prior to treatment start date;
- If Day is missing and Month and Year \neq Month and Year of treatment start date, then set to first of the month;
- If start date is completely missing, set to treatment start date, as long as adverse event end date is not prior to treatment start date.

If end date of an adverse event is partially missing, impute as follows:

- If both Month and Day are missing, then set to December 31;
- If only Day is missing, then set to last day of the month;
- If end date is completely missing, do not impute.

4.4.3. Concomitant Medications

When the start date or end date of a medication is partially missing, the date will be imputed to determine whether the medication is prior or concomitant (or both). The following rules will be applied to impute partial dates for medications:

If start date of a medication is partially missing, impute as follows:

- If both Month and Day are missing, then set to January 1;
- If only Day is missing, then set to the first of the month;

If end date of a medication is partially missing, impute as follows:

- If both Month and Day are missing, then set to December 31;
- If only Day is missing, then set to last day of the month;

If start date or end date of a medication is completely missing, do not impute.

5. PATIENT POPULATION

5.1. Patient Disposition

The number of patients for each of the following categories will be summarized by treatment group:

- All randomized patients;
- Number and percentage of patients in the safety population;
- Number and percentage of patients who did not receive study treatment;
- Number and percentage of patients who completed 48 weeks of study treatment;
- Number and percentage of patients who prematurely discontinued study treatment and reasons for treatment discontinuation;
- Number and percentage of patients who participated in testosterone recovery follow-up.

Patient disposition will be summarized for all randomized patients.

5.2. Screen Failure

Reasons for screen failure will be summarized. Number and percentage of patients who did not pass screening will be based on the patients who signed the informed consent form but were not randomized.

5.3. Protocol Deviations

Protocol deviations will be categorized as important protocol deviation or protocol deviation according to the protocol deviation plan. Important protocol deviations will include but not be limited to the following:

- Patients who did not satisfy key entry criteria;
- Patients who met withdrawal criteria during the study but were not withdrawn;
- Patients who received the wrong treatment;
- Patients who received a prohibited concomitant medication that met criteria for an important protocol deviation.

Important protocol deviations will be summarized by deviation category for all patients in the mITT population. A by-patient listing of important protocol deviations will be provided.

Patient eligibility including inclusion criteria that are not met and exclusion criteria that are met at enrollment will be summarized for all patients in the mITT population.

A selected subset of the important protocol deviations that are likely to affect analysis of efficacy will be identified to define the per-protocol population prior to the database lock. This subset will include but will not be limited to the following important protocol deviations:

- Did not satisfy key entry criteria;

- Drug compliance < 75% over more than 1 consecutive month;
- Patient received prohibited concomitant medications that met criteria for important protocol deviations.

5.4. Demographics and Baseline Characteristics

Demographics and baseline characteristics for patients in the mITT population will be summarized by treatment group.

Demographics will include age, race, ethnicity and geographic region while baseline disease characteristics will include clinical disease stage, baseline PSA, presence of metastatic disease, and Eastern Cooperative Oncology Group (ECOG) status.

5.5. Medical History

Medical history will be coded using the Medical Dictionary for Regulatory Activities (MedDRA) and will be summarized by system organ class and preferred term.

In addition, summaries will be provided of medical and surgical treatment history specific to prostate cancer.

5.6. Prior and Concomitant Medications

Prior and concomitant medications taken during the study treatment period will be summarized for all patients in the mITT population by treatment group. Medications are considered concomitant if medications were used during the study treatment period. Medications will be coded using the World Health Organization (WHO) Drug Dictionary and summarized according to the Anatomical Therapeutic Chemical (ATC) Classification System and generic medication name.

Use of antiandrogens initiated during the first 4 weeks of study treatment (including bicalutamide, flutamide, nilutamide, and enzalutamide) will be summarized separately.

5.7. Prior and Current Procedures

Prior and current procedures, including radiotherapies, taken during the study treatment period will be summarized by treatment group for all patients in the mITT population. Procedures are considered current if they occur at or after the date of the first dose of study treatment.

6. STUDY DRUG EXPOSURE AND COMPLIANCE

Patients in the safety population will be summarized for extent of exposure and compliance of study drug by actual treatment received. Study drug exposure will be calculated based on the case report form (CRF) pages of “Relugolix Dosing Log” and “Leuprolide Acetate Administration.” Compliance for relugolix will be based on the CRF of “Study Drug Accountability.”

Summary statistics on extent of exposure and compliance will be provided as follows:

- Treatment duration in weeks;
- Cumulative dose administered (mg) for leuprolide and total tablets taken for relugolix;
- Dose intensity and relative dose intensity for leuprolide;
- Compliance for relugolix.

For leuprolide acetate arm:

Treatment duration in weeks = (the date of last dose – the date of first dose + 84) / 7.

Cumulative dose administered will be sum of all the doses administered.

Dose intensity = cumulative dose administered / ceiling function of (treatment duration in weeks/12).

Relative dose intensity = (dose intensity / 22.5 or 11.25 mg per treatment on Day 1) × 100.

For relugolix arm:

Treatment duration in weeks = (the date of last dose – the date of first dose + 1) / 7.

Relugolix compliance will be calculated as follows:

(total tablets taken / total tablets expected to be taken) × 100.

The total tablets taken will be calculated as:

total number of tablets dispensed - total number of tablets returned.

The total tablets expected to be taken will be calculated as:

3 tablets on Day 1 + 1 tablet per day × (treatment duration in Days -1).

In the case of unreturned bottles, tablets that were dispensed will be assumed to be taken. However, for patients who did not return for their last scheduled visit, tablets that were dispensed and not returned will be subtracted from both the total tablets taken and the total tablets expected to be taken in the calculation of relugolix compliance. In cases when the patient never returned any of the dispensed bottles, the total tablet taken, total tablets expected to be taken, and relugolix compliance will be set to “not able to calculate.”

Summary statistics of relative dose intensity and study drug compliance (eg, mean, median, etc) will be presented along with a categorical summary (eg, < 80%, 80 to 100%, > 100%).

For this study, any dose of relugolix > 240 mg within a 24-hour window is an overdose, except for the 360-mg loading dose on Treatment Day 1. Events of overdose will be reported within 24 hours using a serious adverse event form, whether the overdose is associated with an adverse event or not. Patients with daily dose > 240 mg reported on the relugolix dosing log will be flagged in the listing of study drug administration.

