4. GENERAL CONSIDERATIONS FOR DATA ANALYSES AND HANDLING OF MISSING DATA

4.1. Data Presentation Conventions

Leuprolide acetate injection with 22.5 mg or 11.25 mg (in Japan, Taiwan, and China) every 12 weeks (Q12W) will be presented in total in one column.

All statistical analyses will be conducted using SAS[®] Version 9.2 or higher.

Unless otherwise stated, a statistical test will be assessed at two-sided $\alpha = 0.05$ significance level and all confidence intervals (CIs) will be reported as two-sided.

Where appropriate, variables will be summarized descriptively by study visit. For the categorical variables, the count and proportions of each possible value will be tabulated by treatment group. For continuous variables, the number of subjects with non-missing values and the mean, median, standard deviation (SD), minimum, and maximum values will be tabulated.

Unless otherwise specified, the following conventions will be applied to all analyses:

- Mean and median values will be formatted to one more decimal place than the measured value. Standard deviation values will be formatted to two more decimal places than the measured value, and minimum and maximum values will be presented to the same number of decimal places as the measured value. If the measured value is large (eg, > 100), fewer decimal places may be displayed.
- Percentages will be rounded to one decimal place;
- p-values will be rounded to 4 decimal places. p-values < 0.0001 will be presented as “< 0.0001” and p-values > 0.9999 will be presented as “> 0.9999”;
- 1 month = 30.4375 days. Month is calculated as (days/30.4375) rounded to 1 decimal place;
- 1 year = 365.25 days. Year is calculated as (days/365.25) rounded to 1 decimal place;
- Age = integer part of month (date of randomization – date of birth – X)/12, where X = 1 if day of randomization date < day of birth date and X = 0 otherwise. If only birth year is provided, 1 July of the birth year will be used to calculate age;
- 1 pound = 0.454 kg;
- 1 inch = 2.54 cm;
- Missing efficacy or safety data will not be imputed, unless otherwise specified;
- For laboratory results above or below sensitivity limits displayed as < or > a quantification threshold, 0.000000001 will be subtracted or added, respectively, to the sensitivity limit to derive a numeric result for analyses;
- For safety analyses, calculation of percentages will be calculated on the basis of the number of patients in the analysis population in each treatment group;

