7.3.1.2. Kaplan-Meier Analysis and Censoring Rules

In general, patients with testosterone escape (any testosterone test result rising above the castration level [≥ 50 ng/dL]) from Week 5 Day 1 through Week 49 Day 1 will be considered as an event in the Kaplan-Meier analysis. The time from the date of the first dose to date of the first testosterone escape will be considered as the event time.

Patients who have not reached castration level at Week 5 Day 1 will be considered as having had an event at the target day of Week 5 Day 1.

Patients who discontinued from the study prior to Week 5 Day 1 will be censored at the target day of Week 5 Day 1. In addition, patients without a Week 5 Day 1 assessment will be considered to have had an event at the target day of Week 5 Day 1.

For patients reaching castrate levels at Week 5 Day 1, the following rules will be applied to the Kaplan-Meier analysis for estimation of sustained castration rate with consideration for missed visits. Time to event or censoring, whichever occurs first, will be used in Kaplan-Meier analysis.

- a) Patients who had one or more consecutive missed visits (ie, a visit gap of > 42 days) and had a non-castrate assessment immediately after the missed visit(s) will be considered as having an escape at the target day of the earliest missed visit prior to the non-castrate assessment;
- b) Patients with one missed visit who has a castrate assessment immediately before and after the missed visit will be assumed to be castrated at the missed visit;
- c) Patients with two or more consecutive missed visits (ie, a visit gap of > 70 days) and who had a castrate assessment immediately before and after the missed visits will be censored at the last available testosterone assessment prior to the missed visits.

Note: A visit gap of 70 days for two missed visits was used to consider the duration between two expected visits (8 weeks), plus the visit windows allowed per protocol (7 days for each

expected visit with a total of 2 weeks as visit window for two visits). A visit gap of 42 days for one missed visit was used to consider the visit of every 4 weeks, and ± 7 days as the visit window, per protocol.

Otherwise, patients will be censored at the last available assessment prior to the follow-up visits, including patients who discontinue from the trial for reasons other than a non-castrate testosterone level.

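### The leuprolide dose-intensity formula rounds the number of 12-week intervals up, so a last injection even one day late scores full dosing as 80%, 75% or 66.7% (four, three or two injections)

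*SAP*

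**What the plan says.** SAP Section 6 builds the leuprolide exposure measure in four steps:

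- Duration: "Treatment duration in weeks = (the date of last dose – the date of first dose + 84) / 7".
- Total dose: "Cumulative dose administered will be sum of all the doses administered".
- Dose intensity: "Dose intensity = cumulative dose administered / ceiling function of (treatment duration in weeks/12").
- Relative dose intensity: "Relative dose intensity = (dose intensity / 22.5 or 11.25 mg per treatment on Day 1) × 100".

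The result is summarized by mean, median and similar statistics, and in categories given as examples: below 80%, 80 to 100%, and above 100%. Section 6 states no tolerance for injection timing.

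The schedule is set elsewhere. Section 4.1 has "Leuprolide acetate injection with 22.5 mg or 11.25 mg (in Japan, Taiwan, and China) every 12 weeks (Q12W"), and Section 4.3.3 has "The treatment period per protocol is 48 weeks (Treatment Day 336"), which implies four injections. Section 4.3.1 defines the date of last dose as the day that dose is received, and Section 4.3.4 repeats the 84-day addition.

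**The concern.** A ceiling makes sense when follow-up can stop partway through a dosing interval. Here the added 84 days always complete the last interval, so a patient dosed exactly on schedule lands on an integer. That is the worst place to apply a ceiling: one day beyond it adds a whole interval to the denominator, while nothing is added to the numerator.

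The measure then cannot separate minor scheduling slack from a missed depot injection, which is what relative dose intensity should show. Relugolix compliance in the same section is a ratio of tablets taken to tablets expected, with no such rounding, so only the comparator arm is affected. Evaluation Criterion 2 is a noninferiority comparison with leuprolide, and a reader who wants to know whether the comparator was properly delivered will look at this table.

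**Working it through.** **Inputs.** Interval 84 days (Section 4.1); duration and dose-intensity formulas (Section 6); last dose = day of the last injection (Section 4.3.1). The SAP states no dose-intensity figure to reproduce. As a check on the reading, four on-time injections give (252 + 84)/7 = 48 weeks, which matches Section 4.3.3.

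**Formula.** For *k* injections, with the last one *s* days after first dose + 84(*k* − 1) days:

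- duration in days = 84(*k* − 1) + *s* + 84 = 84*k* + *s*
- relative dose intensity as written = 100 × *k* / ceiling((84*k* + *s*)/84)

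The Day 1 dose cancels, so 22.5 mg and 11.25 mg give the same percentages.

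| Injections | Last injection | Days | Days/84 | Ceiling | As written | Unrounded | Nearest integer |
|---|---|---|---|---|---|---|---|
| 4 | 7 days early | 329 | 3.917 | 4 | 100% | 102.1% | 100% |
| 4 | 1 day early | 335 | 3.988 | 4 | 100% | 100.3% | 100% |
| 4 | on time | 336 | 4.000 | 4 | 100% | 100% | 100% |
| 4 | 1 day late | 337 | 4.012 | 5 | 80.0% | 99.7% | 100% |
| 4 | 7 days late | 343 | 4.083 | 5 | 80.0% | 98.0% | 100% |
| 3 | 1 day late | 253 | 3.012 | 4 | 75.0% | 99.6% | 100% |
| 3 | 7 days late | 259 | 3.083 | 4 | 75.0% | 97.3% | 100% |
| 2 | 1 day late | 169 | 2.012 | 3 | 66.7% | 99.4% | 100% |
| 2 | 7 days late | 175 | 2.083 | 3 | 66.7% | 96.0% | 100% |

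In milligrams, four injections of 22.5 mg with the last one day late give 90/5 = 18.0 mg per interval instead of 90/4 = 22.5 mg.

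**Direction.** A ceiling is never below its argument, so the value as written is never above the unrounded one. A delay of 1, 7 or 14 days costs the same full interval. A patient with a single injection scores 100%.

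**Loss of meaning.** A patient who missed one of four injections, with the last on time, scores 3/4 = 75%. A patient given all three injections due, with the last one day late, also scores 75%.

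**How many patients.** The SAP gives no injection window. Section 7.3.1.2 refers to ± "7 days as the visit window, per protocol", but for the four-weekly visits. Two scenarios for four-injection patients:

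- All last injections on time or early: none affected.
- Assumed uniform over the 15 days from −7 to +7: 7/15 = 47% are late and score 80%. The mean is (8/15) × 100 + (7/15) × 80 = 90.7%, about 91%.

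**The case against.** The strongest reply is that little depends on this number. Relative dose intensity enters no hypothesis test and no censoring rule. Treatment duration and cumulative milligrams are summarized in the same section, so a four-injection patient still shows 90 mg (or 45 mg) over about 48 weeks. That stands, and it limits the point to a descriptive summary in one arm.

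Some stronger readings are tempting, but the SAP does not support them:

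- *The report will show an under-dosed control arm.* This depends on when last injections were given. Only net delay relative to the first dose counts, and a late earlier injection that is made up by the last one has no effect. The 47% and 91% figures rest on an assumed spread.
- *Fully dosed patients fall below 80%.* Four-injection patients with a late last dose score exactly 80.0% and stay in the 80 to 100% category. Only patients with two or three injections drop below it, and the cut-points are themselves only examples.
- *Per-protocol membership is distorted.* Section 5.3 uses drug compliance below 75%, but Section 6 defines compliance for relugolix only and treats relative dose intensity as a separate measure. Nothing links the two.
- *Even on-time patients score 80%.* The note under Table 2 treats the leuprolide last-dose date as ending 12 weeks after the last injection. Carried into Section 6, this would count 84 days twice: (252 + 84 + 84)/84 = 5. That note belongs to the visit windows. Section 4.3.1 defines the date as the day of receipt, which is the only reading under which adding 84 makes sense.

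**Conclusion.** The formula as written is wrong for its purpose. Any net delay of the last injection, even one day, adds an interval in which no injection was due. Relative dose intensity becomes 80.0%, 75.0% or 66.7% for four, three or two injections, where one day late should give 99.4% to 99.7%. These percentages follow from the SAP alone, and nothing elsewhere in it supplies a tolerance.

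The error always runs towards understating leuprolide exposure. It affects the mean and median, and it affects the below-80% category only for patients with two or three injections. Its overall size cannot be fixed from the document: it runs from near zero to the 47% of the uniform ±7-day scenario, and that scenario is an illustration, not an upper limit. No efficacy conclusion is affected. It is worth correcting because the change is small and the figure bears on how delivery of the comparator is read.

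**What to change.** Replace the ceiling with rounding to the nearest integer, so that the denominator is the number of injections scheduled up to and including the last one given. All the late cases in the table then score 100%, and a patient who truly missed one of four injections with the last on time still scores 75%. The price is that net delays under about 42 days are no longer reflected. Treatment duration, reported alongside, still shows them.

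The alternative is the unrounded duration in weeks divided by 12, which keeps small delays visible. Its side effect is that a last injection 1 to 7 days early gives 336/335 to 336/329, or 100.3% to 102.1%, for four injections. The above-100% cut-point would then need a small tolerance, so that these patients are not labelled as over-dosed.

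Either choice is a one-line change to Section 6 and to the exposure program. It touches no dosing rule, endpoint or test.

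### For relugolix men who miss their last visit, the compliance rule subtracts all unreturned tablets from a day count that holds only part of them, so compliance is biased upward whenever dosing stopped before that supply ran out

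*SAP*

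**What the plan says.** SAP Section 6 defines relugolix compliance as tablets taken over tablets expected, times 100.

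- Taken is "total number of tablets dispensed - total number of tablets returned".
- Expected is "3 tablets on Day 1 + 1 tablet per day × (treatment duration in Days -1"), where duration runs from first to last dose (also Section 4.3.4).
- Section 4.3.1 fixes the end point: "The date of the last dose of study drug is defined as the date a patient receives the last dose of study drug".
- The default for missing bottles is: "In the case of unreturned bottles, tablets that were dispensed will be assumed to be taken".
- For patients who missed their last scheduled visit there is an exception: "tablets that were dispensed and not returned will be subtracted from both the total tablets taken and the total tablets expected to be taken".
- A patient who never returned any bottle is set to not calculable.

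Results are summarised by mean and median and in categories such as below 80%, 80 to 100% and above 100%. Section 5.3 separately lists, among the deviations that define the per-protocol population, "Drug compliance < 75% over more than 1 consecutive month".

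**The concern.** The two subtractions do not match. Taken is built from tablets dispensed, so it contains every unreturned tablet, and removing them is coherent. Expected is built from days, and the number dispensed does not enter it. It holds only those days of the unreturned supply that fall on or before the last dose. Subtracting the whole supply therefore also removes days on which tablets from earlier, returned bottles were due.

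The error goes one way when dosing stops early, arises in one arm, and is confined to men without a final accountability visit. It can put implausible values into the mean and move poor compliers into a better category.

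The wording adds a second problem. Tablets dispensed and not returned is also Section 6's own definition of tablets taken. Read strictly, the numerator becomes zero for every such man, so the programmer has to guess that whole unreturned bottles are meant.

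**Working it through.** The SAP gives no compliance figure, so there is nothing to reproduce. The check puts the Section 6 formulas through worked cases.

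**Inputs from the SAP.** Taken, expected and duration are as above; visit days come from Table 2.

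**Assumptions.** Bottle size and dispensing interval are not in the SAP. I take U = 30 unreturned tablets as the main case, with 28, 35 and 60 as a range.

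**Notation.** D = day of the last attended visit, A = tablets due before it, a = true adherence up to it, k = days dosed afterwards from the unreturned supply.

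**Formula.**
- Due before the visit (Days 1 to D−1): A = 3 + (D−1−1) = D + 1.
- Duration = D − 1 + k, so expected = 3 + (D−1+k−1) = A + k.
- Taken before the exception = aA + U.
- After subtracting U from both: compliance = aA / (A + k − U).

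This equals a only when k = U. For k < U with a positive denominator it is too high. The denominator is zero when duration = U − 2 (last dose on Day 28 for U = 30) and negative below that.

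**Full complier (a = 1), U = 30:**

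| Last visit | A | k = 0 | k = 5 | k = 15 | k = 30 |
|---|---|---|---|---|---|
| Day 29 | 30 | 30/0, undefined | 30/5 = 600% | 30/15 = 200% | 100% |
| Day 57 | 58 | 58/28 = 207% | 58/33 = 176% | 58/43 = 135% | 100% |
| Day 85 | 86 | 86/56 = 154% | 86/61 = 141% | 86/71 = 121% | 100% |
| Day 169 | 170 | 170/140 = 121% | 170/145 = 117% | 170/155 = 110% | 100% |
| Day 309 | 310 | 310/280 = 111% | 310/285 = 109% | 310/295 = 105% | 100% |

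**Other supply sizes, full complier, k = 0:**
- Day 57: U = 28 gives 58/30 = 193%; U = 35 gives 58/23 = 252%; U = 60 gives 58/(−2), a negative denominator.
- Day 309: U = 28 gives 310/282 = 110%; U = 35 gives 310/275 = 113%; U = 60 gives 310/250 = 124%.

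**Poor compliers, U = 30:**
- 70% adherent, Day 169: k = 0 gives 119/140 = 85%, which moves him from below 80% to 80 to 100%. With k = 15 he scores 119/155 = 76.8% and stays below 80%.
- 70% adherent, Day 309, k = 0: 217/280 = 77.5%, still below 80%.
- 60% adherent, k = 5: Day 85 gives 51.6/61 = 84.6%, which changes category; Day 113 gives 68.4/89 = 76.9%, which does not.

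**Existing guard.** It covers only men who never returned a bottle. The man last seen at Day 29 has returned his first bottle, so his ratio is computed. The SAP gives no cap, no floor and no rule for setting the last-dose date of a man who does not come back. If that date defaults to about the last attended visit, k is near 0, the worst column.

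**The case against.** The case for leaving the rule alone has several parts, and much of it limits the point.

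- A reader might infer that the expected count contains none of the unreturned supply. It does not say that: it contains k days of it, and for a man who used all of it (k = U) the rule is exact.
- A reader might take values of several hundred percent as typical. They need early dropout. For U = 28 to 35 and k = 0, a full complier last seen at Day 309 scores 110 to 113%.
- A reader might infer that poor compliers escape the 75% cut and so distort the per-protocol set. Section 5.3 sets that criterion over a period of more than a month and does not tie it to the whole-treatment percentage of Section 6. Section 4.2.2 also drops the per-protocol analysis if that population is above 95% or below 50% of the mITT population.
- A reader might apply the 15% dropout assumption of Section 2.2 to 610 men (0.15 × 610 = 91.5, about 92) and call them all affected. Only those who missed the last scheduled visit, returned at least one bottle and had k < U are affected. The SAP refers to end-of-treatment visits, so a man who drops out may still have his tablets counted. The number affected cannot be derived from the SAP.
- No primary or key secondary test uses this compliance figure.

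All of these stand as limits on size and reach. None makes the formula right when k < U.

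**Conclusion.** The rule is wrong as written for relugolix men who missed their last scheduled visit, returned at least one bottle, and stopped dosing before the unreturned supply would have run out. Compliance is then overstated or, after early dropout, undefined or negative. The direction follows from the SAP's formulas alone. The size rests on the assumed supply and on k: with U = 30 and k = 5, a full complier scores from 176% (last seen Day 57) down to about 109% (Day 309), and larger supplies give larger errors. The effect established is on the descriptive compliance mean and category table. Nothing in the SAP shows an effect on the per-protocol population or on any efficacy conclusion. It should be corrected because the derivation gives wrong values and the repair is cheap.

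**What to change.** For these men, compute both counts over one interval: from first dose to the earlier of the last dose and the day before the last drug-accountability visit.

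- Taken = tablets dispensed before that visit minus tablets returned. Earlier unreturned bottles stay assumed taken under the existing default; only supply dispensed at or after that visit is excluded.
- Expected = 3 + (days in that interval − 1), with no tablets subtracted. Equivalently, subtract from the expected count only the k days that fall inside the treatment duration.

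The result is aA/A = a in every case above.

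The default for earlier bottles must be kept. Take a fully adherent man last seen at Day 85 who was dispensed 90 tablets before that visit, lost one earlier bottle of 30 and returned 4 tablets. Counting only accounted-for bottles gives (60 − 4)/86 = 65%; keeping the default gives (90 − 4)/86 = 100%.

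The SAP should also define dispensed and not returned at bottle level, and state how the last-dose date is set for men who do not come back.

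Cost: a short edit to Section 6 and one derivation. Compliance after the last accountability visit is not described for these men, and some reported values will fall.
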